7.4 Visits during study treatment

Visits V1 until V10 are planned to be performed as outlined in **Table 8**, including visit windows of +/- 2 days if nothing else stated in **Table 8** regarding specific items.

Study treatments are to be administered as outlined in [Section 4.3](#), [Section 6.3](#), and [Section 6.4](#), and **Table 8**.

Measurements/assessments/sampling as outlined below are to be done before administration of study treatments if scheduled for the same day, if no other specific order of events is defined.

At all planned visits for treatments during the treatment period (see **Table 8**), the following items should be assessed and documented:

- concomitant medications/treatments,
- weight, and ECOG performance status (see [Section 12.1](#)),
- vital signs including temperature, blood pressure (BP), and heart rate (HR) (BP and HR will be measured according to local standard practice); [REDACTED]
[REDACTED]
[REDACTED]
- major body systems via physical examination; [REDACTED]
[REDACTED]
[REDACTED]
- safety blood samples for hematology, coagulation, serum chemistry, and urinalysis, to be performed and evaluated locally (as detailed in [Section 7.3](#)), and
- adverse events according to NCI-CTCAE v5.0.

The following items should be assessed/done and documented at the visits specified below (see also **Table 8**):

- [REDACTED]
[REDACTED]
[REDACTED]
[REDACTED]
- [REDACTED]
[REDACTED]
- [REDACTED]
[REDACTED]
- [REDACTED]
[REDACTED]
- [REDACTED]
[REDACTED]
[REDACTED]
[REDACTED]
[REDACTED]
- [REDACTED]
[REDACTED]
[REDACTED]
[REDACTED]
[REDACTED]
- [REDACTED]
[REDACTED]
[REDACTED]
- [REDACTED]
[REDACTED]
[REDACTED]
- [REDACTED]
[REDACTED]
[REDACTED]

7.5 Post-treatment safety visits

Thirty days (-0/+4 days) after the last administration of trial treatment, a safety visit should be done for all patients,

The visits should if possible be held as planned, but there are patient individual circumstances that might prevent a personal visit to the site, e.g. the patient might be in medical care at another hospital and in a medical status not amenable to transportation. In such cases, the Investigator should try collecting as much of the normally collected information as possible from the sources available.

The items to be assessed/collected at visit are (see also **Table 8**):

- concomitant medications/treatments,
- weight, and ECOG performance status (see [Section 12.1](#)),
- vital signs including temperature, blood pressure (BP), and heart rate (HR) (BP and HR will be measured according to local standard practice);
- major body systems via physical examination;
- safety blood samples
- a 12-lead electrocardiogram (ECG) will be recorded according to local site standard procedures,
- for women of childbearing potential, a highly sensitive serum pregnancy test should be performed, and
- adverse events according to NCI-CTCAE v5.0.

7.6 Visits during post-treatment follow-up

7.6.1 *Post-treatment visits before determination of relapsed disease*

Patients who have permanently stopped all study treatment without having had confirmation of relapsed disease will be followed

At these timepoints the following is to be done (see also **Table 8**):

- CT scanning is to be done every 3-6 months per standard of care for the patient's stage of CRC disease (See [Section 1.1](#) regarding recommendations for surveillance after curative treatments); collection of information from a protocol perspective should be done until scan documented relapse of disease (or until other

anti-cancer treatment would be started before confirmed progressive disease), or for a maximum of 3 years from first study treatment in the individual patient,

- [REDACTED] continue ctDNA testing per local standard of care; collection of information from a protocol perspective should be done until scan documented relapse of disease (or until other anti-cancer treatment would be started before confirmed progressive disease), or for a maximum of 3 years from first study treatment,
- [REDACTED]
- [REDACTED]
- [REDACTED]
- documentation of safety; [REDACTED]
- if applicable, for female patients of childbearing potential, a serum pregnancy test will continue to be done on a monthly basis until 6 months after study treatments have been stopped, if not a new anti-tumor treatment has been initiated earlier in which case the study related testing will be terminated at the time of start of new anti-tumor treatment, and
- if applicable, collection of information regarding further anti-cancer treatments.

[REDACTED]

7.6.2 Post-treatment visits after determination of relapsed disease

Patients who have permanently stopped all study treatment and have had confirmation of relapsed disease will be followed [REDACTED]

If the patient is unable to attend a site visit, follow-up via a telephone contact is acceptable.

At these timepoints the following is to be done (see also **Table 8**):

- assessment of survival status [REDACTED]
- documentation of safety; [REDACTED]
- if applicable, for female patients of childbearing potential, a serum pregnancy test will continue to be done on a monthly basis until 6 months after study treatments have been stopped, if not a new anti-tumor treatment has been initiated earlier in which case the study related testing will be terminated at the time of start of new anti-tumor treatment, and
- collection of information regarding further anti-cancer treatments.

7.7 Safety assessments

Safety and tolerability of EO2040 in combination with nivolumab will be assessed by incidences of AEs, TEAEs, SAEs, deaths, reasons for treatment discontinuation/delays, and laboratory abnormalities. Adverse events will be categorized by their system organ class (SOC) and preferred term (PT) using the current MedDRA version and graded according to NCI-CTCAE v5.0 [100].

The trial safety setup is described in [Section 4.3](#), the specific safety parameters to be monitored/assessed are outlined in [Section 7](#), and safety monitoring procedures of the trial are described in [Section 8](#). The timing of assessments is also described in **Table 8**.

Clinical laboratory analyses as described in [Section 7](#) will be performed by a local laboratory. More frequent evaluations may be performed at the Investigator's discretion if medically indicated; results of such evaluations should also be recorded in the eCRF. Normal ranges for all utilized local laboratories should be provided by the sites to the Sponsor.

7.8 Efficacy assessments

[figure not shown]
Response to therapy will be measured with a standard-of-care, CLIA certified ctDNA assay at the evaluation times specified in **Table 8**.

Identification of somatic mutations in the blood will be confirmed by sequencing of the resected tumor using a CLIA-certified next-generation sequencing panel. Clearance of ctDNA will be characterized by the disappearance of all somatic mutations identified in the blood, as well as no appearance of any additional new somatic mutations.

The primary endpoints will enumerate patients who have clearance of ctDNA, AND do not have any radiographic evidence of recurrence at 6 months.

Secondary endpoints include assessments of tumor recurrence (the word relapse is used interchangeably with recurrence) via scanning (preferably CT, but MRI is accepted if local SOC; in any case method to be used as consistently as possible in an individual patient throughout the study) or other evaluations such as endoscopy.

The best overall response is the best response recorded from the start of the treatment until disease recurrence. The patient's best response assignment will depend on the achievement of both ctDNA and imaging criteria (see **Table 9**).

7.9 Primary immunological assessments

7.9.1 Cell mediated immunity

Cell-mediated cytotoxicity is a key element in the proposed mechanism of action of the peptides composing EO2040.

Selection of an ex-vivo monitoring technique that provides a good measure of immune reactivity is important in determining potential correlations between clinical and immunologic responsiveness to specific immunotherapy.

Cellular immune response in this trial will be evaluated. Samples will be collected at screening and during the trial according to **Table 8**.

An important exploratory endpoint of the trial is the assessment of the percentage of patients with shown immunogenicity (expansion of specific T cells comparing samples taken at baseline versus on treatment in an individual patient determining if the patient has a positive response to the immunization, or not) in relation to the peptides that compose EO2040. Cross reactivities with the corresponding nominal peptides from BIRC5 and FOXM1 will also be evaluated.

As exploratory objectives of the trial, additional scientific information related to characterization of factors impacting antitumor immunity will be searched for with the intention to explore their influence on safety and/or efficacy parameters.

Preparation/shipping procedures for blood samples will be detailed in the Laboratory Manual; a central laboratory will handle the cellular immune response analyses.

7.9.2 Correlations between immunogenicity and other trial outcome parameters

As an exploratory objective, statistical assessments of correlations between immunogenicity [REDACTED] of the components of EO2040 [REDACTED], and efficacy and safety outcome parameters will be conducted. Cross reactivities shown for the nominal antigens BIRC5 and FOXM1 will also be explored in the same way.

7.10 Assessments for other exploratory endpoints

Exploratory endpoints are outlined in [Section 3.2.3](#), beside what has already been described in [Section 7.9](#), the following assessment types are going to be utilized:

- [REDACTED]
- [REDACTED]
- [REDACTED]
- [REDACTED]
- [REDACTED]
- [REDACTED]

For all parameters described above, when possible, the intention is to explore their influence on safety and efficacy outcome parameters of the patients in the trial.

8 SAFETY MONITORING

8.1 Safety monitoring definitions

8.1.1 Adverse events

International Council for Harmonization (ICH) guideline E2A defines an AE as “any untoward medical occurrence in a patient or clinical investigation subject administered a pharmaceutical product and which does not necessarily have to have a causal relationship with this treatment”.

According to the FDA (21CFR312.32), an AE means any untoward medical occurrence associated with the use of a drug in humans, whether, or not, considered drug related.

An AE can therefore be any unfavorable and unintended sign (e.g. tachycardia, enlarged liver), symptom (e.g. nausea, chest pain), abnormal result of an investigation (e.g. laboratory finding), or disease temporarily associated with the use of a medicinal product, whether or not considered related to the medicinal product.

8.1.2 Serious Adverse events

A serious adverse event (SAE) is any untoward medical occurrence that at any dose fulfills one or more of the following criteria:

- results in death,
- is immediately life-threatening,
 - *the term “life-threatening” in the definition of “serious” refers to an event in which the patient was at immediate risk of death at the time of the event; it does not refer to an event which hypothetically might have caused death if it were more severe,*
- results in persistent or significant disability/incapacity,
 - *disability is defined as a substantial disruption in a person’s ability to conduct normal life functions (i.e. the AE resulted in a significant, persistent, or permanent change, impairment, damage, or disruption in the patient’s bodily function/structure, physical activities, or quality of life),*
- is a congenital anomaly/birth defect,
- requires inpatient hospitalization or prolongation of existing hospitalization, and
 - *a hospitalization is defined as an inpatient overnight stay, but this can be shorter than 24 hours,*
- is another medically significant event defined as an event that may not be immediately life-threatening or result in death or hospitalization but may jeopardize the patient or may require intervention to prevent any of the above listed outcomes.

8.1.2.1 Excluded events

Hospitalization for the following reasons will not be regarded as serious (i.e. will not be immediately reportable):

- routine treatment or monitoring of the disease under study, including hospitalization due to trial-related procedures, not associated with any deterioration of the patient’s status,

- elective or pre-planned treatment (before signing the ICF) for a pre-existing condition that is unrelated to the disease under study and has not worsened since signing the ICF,
- treatment on an emergency outpatient basis for an event not fulfilling any of the definitions for an SAE and not resulting in hospital admission,
- underlying disease progression (the CRC which is the basis for the patient enrollment in the trial) and events which are unequivocally (without doubt) related to the disease progression, and
- social reasons, respite care, and in the absence of a medical condition.

In addition, as also outlined in [Section 8.5.1](#), progression of the underlying disease or an AE unequivocally (without doubt) related to the progression of the underlying disease, regardless of its outcome or seriousness criteria, does not need to be reported as a SAE. However, the medical conditions and underlying diseases associated with disease progression needs to be captured on the AE eCRF page (as a non-serious AE). An SAE must be reported only if there are clinical symptoms/signs that cannot be without doubt associated with the progression of the underlying disease.

8.1.3 Suspected Unexpected Serious Adverse Reactions (SUSARs)

SUSARs are serious events that are not listed in the Reference Safety Information section of the EO2040 Investigator Brochure and are related to the study drug. Suspected adverse reaction means any AE for which there is a reasonable possibility that the study drug caused the AE. For the purposes of Investigational New Drug safety reporting, “reasonable possibility” means there is evidence to suggest a causal relationship between the study drug and the AE.

8.1.4 Severity/intensity versus seriousness

ICH E2A: The term “severe” is often used to describe the intensity (severity) of a specific event (as mild, moderate, or severe myocardial infarction); the event itself, however, may be of a relatively minor medical significance (such as a severe headache). This is not the same as “serious”, which is based on patient/event outcome or action criteria usually associated with events that pose a threat to a patient’s life or functioning. Seriousness (not severity) serves as a guide for defining regulatory reporting obligations.

8.2 Pregnancies

If not surgically sterile, female patients of childbearing potential age must use highly effective contraception from signing the ICF through 6 months after the last treatment dose administered (see [Section 5.1](#)).

If not surgically sterile, male with female partner of childbearing potential age must use condom from signing the ICF through 6 months after the last treatment dose administered. Males must also ensure that their partners of childbearing potential use highly effective contraception (see [Section 5.1](#)).

Pregnancy is not considered an AE unless it meets any criteria for becoming serious (see [Section 8.1.2](#)). However, it is the responsibility of the Investigator or their designee to report immediately any pregnancy in a patient or the patient’s sexual partner that occurs during the

study (see [Section 8.5.3](#) regarding reporting procures). All patients who become pregnant must immediately discontinue the study drug and be withdrawn from study treatment.

The Investigator should make every effort to follow the patient until completion of the pregnancy and provide the corresponding information by the mean of a SAE/Pregnancy form within 2 weeks from awareness (see [Section 8.5.3](#)). The Sponsor Safety Group will periodically request from the investigator targeted follow-up information using a specific Pregnancy Follow-up form. If the events during pregnancy and/or outcome of pregnancy (i.e. complications regarding mother/baby) meet the criteria for classification of an SAE, the Investigator must follow the procedures for SAE reporting.

8.3 Safety monitoring periods

8.3.1 Reporting

In patients exposed to study treatment, the following must be reported from the date of the patient's signing the ICF until 30 days after the final administration of study treatment:

- AEs regardless of their causal relationship to study treatment,
- SAEs without a plausible causal relationship to study treatment, and
- pregnancy of the patient or the patient's sexual partner.

SAEs with a plausible causal relationship to study treatment must be reported from the date of the patient's signing the ICF until indefinitely (regardless of the time elapsed from the final study treatment administration).

In patients not exposed to study treatment, the reporting period for AEs (including SAEs regardless of causal relationship) starts with signature of the ICF and ends:

- the date of the Investigators assessment of "screen failure"-status (see [Section 5.3.2](#)), or
- the date of the patient's consent withdrawal.

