vaccine by itself, or with a delayed start of nivolumab, would also be efficacious. If this would be the case, one would potentially be able to spare patients the risk of some adverse events linked to nivolumab. Of note, neither the trial investigators, nor the Sponsor, considers it adequate to reverse the order of the cohorts since the setting argues for an approach directed towards maximum efficacy. Also, with the predetermined relatively short treatment duration it is assumed that the toxicity burden from nivolumab will be limited, and acceptable, considering the setting.

The trial includes, due to the specific characteristics of the combination of EO2040 and nivolumab key well defined strategies for patient management at possible immune-mediated reactions (see [Section 6.4.1](#) and extended treatment algorithms in [Section 12.5](#)).

[REDACTED]

The efficacy assessments by scanning in the trial are based on site/local investigator assessments which is considered adequate for fast decisions regarding study treatments, and in context of key endpoints related to ctDNA testing.

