6.4 Treatment modifications for EO2040 and nivolumab

- [REDACTED]
- [REDACTED]
- [REDACTED]
- [REDACTED]

- [REDACTED]

In case of immune-related adverse events related to EO2040 and/or nivolumab, instructions for treatment modifications as outlined in [Section 6.4.1](#) should be followed.

General criteria for treatment discontinuation and study participation termination are outlined in [Section 5.3](#).

6.4.1 Recommended treatment modifications for EO2040 and nivolumab in case of immune-related adverse reactions

For suspected immune-related adverse reactions, adequate evaluation should be performed to confirm etiology or exclude other causes. Based on the severity of the adverse reaction, the treatment should be withheld, and corticosteroids administered. If immunosuppression with corticosteroids is used to treat an adverse reaction, a taper of at least 1-month duration should be initiated upon improvement. Rapid tapering may lead to worsening or recurrence of the adverse reaction. Non-corticosteroid immunosuppressive therapy should be added if there is worsening or no improvement despite corticosteroid use. **Table 7** shows the recommended treatment management for different immune-related adverse reactions. Regarding management of immune-related adverse reactions due to nivolumab see also the European SmPC or US PI [90, 91].

Regarding nivolumab, patients should be monitored continuously (at least up to 5 months after the last dose) as an adverse reaction with nivolumab may occur at any time during or after discontinuation of therapy. [REDACTED]

Patients will be reviewed on a case-by-case basis, should they need to discontinue EO2040 and/or nivolumab due to toxicity. See [Section 6.4](#), regarding guidance for continuation of individual components of the used compounds in this trial.

[figure not shown]
In case of detected, or suspicious, immune-related adverse reactions it is recommended that the treating physician consult at least one of the following guidance documents for a thorough description regarding possible workup for final diagnosis:

[figure not shown]
- Management of toxicities from immunotherapy: ESMO Clinical Practice Guidelines for diagnosis, treatment and follow-up. *Annals of Oncology* 2017; 28 (Supplement 4): i119–i142 [105]
- Management of Immune-Related Adverse Events in Patients Treated With Immune Checkpoint Inhibitor Therapy: ASCO Guideline Update. *J Clin Oncol* 2021; 39 (36): 4073-4126 [106]

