8.5 Reporting by the investigational site

8.5.1 Adverse events

Any AE (including SAEs), whether, or not considered to be causally related to the trial medication and regardless of its seriousness, must be described and recorded in the AE section of the patient's eCRF on an ongoing basis.

A pre-existing condition is a clinical condition (including a condition being treated) that is diagnosed before the patient signs the ICF and that is documented as part of the patient's medical history; any clinically significant worsening of a pre-existing condition constitutes an AE. Also, any recurrence of a pre-existing condition is an AE.

The questions concerning whether the condition existed before the start of the active phase of the study and whether it has increased in severity and/or frequency will be used to determine whether an event is a TEAE. An AE is considered to be treatment-emergent if it is not present when the active phase of the study begins and is not a chronic condition that is part of the patient's medical history, or it is present at the start of the active phase of the study or as part of the patient's medical history, but the severity or frequency increases during the active phase. The active phase of the study begins at the time of the first dose of the study drug. The active phase of the study ends at the post-treatment visit for safety assessment (see **Table 8**).

A standardized question such as "Have you had any health problems since your last visit or since you were last questioned?" will be given by the Investigator or the investigational site personnel at each contact with the patient.

Progression of the underlying disease or an AE unequivocally (without doubt) related to the progression of the underlying disease, regardless of its outcome or seriousness criteria, does not need to be reported as an AE/SAE. However, the medical conditions and underlying diseases associated with disease progression needs to be captured on the AE eCRF page (as a non-serious AE). An SAE must be reported only if there are clinical symptoms/signs that cannot be without doubt associated with the progression of the underlying disease.

Whenever possible, a diagnosis rather than symptoms should be provided (e.g. anemia instead of low Hb).

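### Mandatory AE reporting and the treatment-emergent window close about 30 days after the last dose, out of step with the protocol's 5-month nivolumab monitoring period and its other AE-recording rules

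*Protocol*

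**What the plan says.** **Reporting window (Protocol 8.3.1).** For treated patients the reporting period runs from "signing the ICF until 30 days after the final administration of study treatment". It covers "AEs regardless of their causal relationship to study treatment", so a non-serious reaction judged related is under the same limit as an unrelated one. Unrelated SAEs are limited in the same way. There is one exception: "SAEs with a plausible causal relationship to study treatment must be reported from the date of the patient's signing the ICF until indefinitely".

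**Treatment-emergent window (Protocol 8.5.1 and 7.5).** "The active phase of the study ends at the post-treatment visit for safety assessment". Section 7.5 sets the timing of that visit: "Thirty days (-0/+4 days) after the last administration of trial treatment, a safety visit should be done for all patients".

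**Nivolumab monitoring (Protocol 6.4.1).** The section says, for nivolumab, that "patients should be monitored continuously (at least up to 5 months after the last dose"), and gives as the reason that a reaction may arise at any time during treatment or after it has stopped. The next sentence is redacted.

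**Other AE-recording duties.** Section 8.3.2 has the investigator look for new AEs at each visit and gives no end date. Section 8.5.1 has any AE, whatever its seriousness, entered in the eCRF on an ongoing basis, with a standard health question at every contact. Sections 7.6.1 and 7.6.2 list a safety-documentation item in follow-up before and after relapse; its detail is redacted in both places.

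**Use of the data.** The first secondary endpoint (3.2.2) is a descriptive profile of AEs, TEAEs, SAEs, deaths, treatment discontinuations and delays, and laboratory abnormalities. Exploratory endpoint 3 (Protocol 3.2.3, SAP 4.2.3) defines its safety variables by TEAEs only. The SAP (3.1, 7.1.1, 7.1.2) states that the study is planned to end with one treated patient, that no tables are produced, and that CRF data are listed as documented.

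**The concern.** The protocol gives its own statement of how long nivolumab reactions should be looked for, and then collects the milder ones for about a fifth of that time. Consider a rash, a thyroid abnormality or a transaminase rise that the investigator thinks is related, needs no hospital admission, and starts in month 3 after the last dose. Section 8.3.1 puts no duty on the site to report it, while 8.3.2 and 8.5.1 read as if it should be recorded. Two sites could handle the same event differently and both could point to the protocol.

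Even if the event is recorded, it falls after the active phase and so would not be a TEAE. TEAE incidence is a named part of the safety endpoint and the whole safety side of the planned correlation with immunogenicity. Late immune reactions, which are of direct interest for a vaccine given with a checkpoint inhibitor, would be absent from that correlation.

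**Working it through.** The plan gives no figure to reproduce here. The check is date arithmetic plus a comparison of sections.

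**1. Length of the monitoring period.** Input: 5 months (6.4.1). With one month = 365.25 / 12 = 30.44 days, 5 × 30.44 = 152.2 days.

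**2. Part outside mandatory reporting of non-serious AEs.** Input: 30 days (8.3.1). 152.2 − 30 = 122.2 days; 122.2 / 152.2 = 80.3%.

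**3. Part outside the TEAE window.** Input: safety visit on day 30 to 34 (7.5, 8.5.1).
- Visit on day 30: 122.2 days, 80.3%.
- Visit on day 34: 152.2 − 34 = 118.2 days; 118.2 / 152.2 = 77.7%.

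Steps 2 and 3 assume that the last nivolumab dose and the final study treatment fall on the same day. If nivolumab stopped earlier, the uncovered part is shorter.

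**4. The two windows against each other.** An event starting on day 31 to 34, before a late safety visit, is inside the active phase (8.5.1) but past the reporting limit (8.3.1). The mismatch is at most 4 days.

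**5. How each type of event starting after the safety visit is treated.**

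| Event | 8.3.1 | 8.3.2 / 8.5.1 recording duties | TEAE |
|---|---|---|---|
| Related SAE | reported, no time limit | recorded | no |
| Related non-serious AE | not required after day 30 | assessed and recorded, no end date | no |
| Unrelated AE or SAE | not required after day 30 | assessed and recorded, no end date | no |

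The last column reads the stated end of the active phase as bounding the whole TEAE definition. The first limb of that definition (not present when the phase begins) does not itself name the end. Without that bound, treatment emergence would have no upper limit.

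**6. Illustration in patients (assumption only).** The documents give no rate or onset times for late non-serious reactions. Suppose 5 to 20% of the 17 planned patients in a cohort had a new one during the 5 months, spread evenly.
- Affected: 17 × 0.05 = 0.85 to 17 × 0.20 = 3.4 patients.
- With onset after day 30: 0.85 × 0.803 = 0.7 to 3.4 × 0.803 = 2.7 patients.

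**The case against.** Several arguments on the other side have force.

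- **Loss of events is not shown.** A reader might infer that late non-serious reactions definitely vanish from the safety endpoint. The documents do not support that. The follow-up safety items in 7.6.1 and 7.6.2, the sentence after the 5-month statement in 6.4.1 and the study schedule are redacted, and any of them may provide for late events. The visible duties in 8.3.2 and 8.5.1 also point towards recording. This stands. What remains is that 8.3.1 sets a limit with no visible exception, so it conflicts with those duties, and that the end of the active phase in 8.5.1 is fully visible.
- **The endpoint is wider than TEAEs.** A late related SAE is still reported and still counts as an SAE. This stands, and it confines the reporting gap for related events to non-serious ones.
- **Section 6.4.1 advises; it does not mandate.** It says patients should be monitored, within a section on recommended treatment modifications, and speaks of nivolumab only. It is clinical vigilance, not a data-collection window. This stands: the text should not be read as a must, and it gives no basis for a 5-month window for patients who receive only the vaccine, or for unrelated SAEs. It is nevertheless the protocol's own statement of when related reactions can be expected.
- **No cohort contrast is biased.** Section 4.5 hopes that with a later regimen "one would potentially be able to spare patients the risk of some adverse events linked to nivolumab", and a reader might conclude that the short window distorts a Cohort 1 versus Cohort 2A difference. The trial is non-comparative, Cohort 2A patients may have nivolumab added after 3 months, and the same window applies to both cohorts. That conclusion is not supported.
- **The SAP makes it nearly moot.** With one treated patient and listings only, no TEAE incidence will be produced. This stands for the current report. An event that was never recorded would still be missing from a listing.

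**Conclusion.** The inconsistency is real and rests on visible text. Sections 8.3.1 and 8.5.1 close the AE-reporting and treatment-emergent windows at day 30 and day 30 to 34. Section 6.4.1 looks at least 5 months ahead for nivolumab reactions, and 8.3.2 and 8.5.1 set recording duties without an end date. About 118 to 122 of roughly 152 days (78 to 80%) lie outside the TEAE window. That percentage is a share of calendar time, not of events.

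A related non-serious reaction starting in that interval would not be a TEAE and may not be recorded. Whether the redacted follow-up items capture it cannot be seen. Related SAEs remain covered by reporting without limit. The 0.7 to 2.7 patients per 17 is an illustration on assumed rates and even onset, not an estimate for this trial. The practical effect on the present SAP is small. The point is a cheap improvement to the protocol as designed and to any later study that reuses its safety sections.

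**What to change.** Reconcile Protocol 6.4.1, 7.6, 8.3.1, 8.3.2 and 8.5.1:

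- For patients who received nivolumab in either cohort, extend the reporting window (8.3.1) and the TEAE window (8.5.1) for AEs suspected to be related to study treatment, whatever their seriousness, to the 5-month period already in 6.4.1. The unlimited reporting of related SAEs stays.
- Keep the existing window of about 30 days for all other AEs.
- Use one closing day for that shorter window in both 8.3.1 and 8.5.1: the date of the safety visit, at the latest day 34.
- Say in 8.3.2, 8.5.1 and 7.6 which events are recorded after that visit, so that the open-ended duties agree with 8.3.1.
- Show events up to the safety visit and after it separately, and flag onset after the start of new anti-cancer therapy. Under the current SAP this means two flags in the AE listing.

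This changes data collection and summary only and adds no new clinical rule. The cost is protocol wording, an eCRF window and a few more AE entries at follow-up contacts that already exist. The AE count may look slightly less favourable.
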